#### [name]

- k. Metformin 2550 mg + glibenclamide 10 mg  $\rightarrow$  metformin 2550 mg + glibenclamide 5 mg
- I. Metformin 2550 mg + glibenclamide 15-20 mg  $\rightarrow$  metformin 2550 mg + glibenclamide 10 mg 14. Taking metformin and glibenclamide, with hypoglycemia or hypoglycemia symptoms, problems with
  - metformin
    - a. Agrees to take metformin
      - i. Metformin 500-850 mg + glibenclamide 2.5 mg  $\rightarrow$  metformin 850 mg
      - ii. Metformin 500-850 mg + glibenclamide 5 mg  $\rightarrow$  metformin 850 mg + glibenclamide 2.5 mg
      - iii. Metformin 500-850 mg + glibenclamide 10 mg  $\rightarrow$  metformin 850 mg + glibenclamide 5 mg
      - iv. Metformin 500-850 mg + glibenclamide 15-20 mg → metformin 850 mg + glibenclamide 10 mg
    - b. Refuses to take metformin
      - i. Metformin 500-850 mg + glibenclamide 2.5 mg  $\rightarrow$  MD consult
      - ii. Metformin 500-850 mg + glibenclamide 5 mg  $\rightarrow$  glibenclamide 2.5 mg
      - iii. Metformin 500-850 mg + glibenclamide 10 mg  $\rightarrow$  glibenclamide 5 mg
      - iv. Metformin 500-850 mg + glibenclamide 15-20 mg  $\rightarrow$  glibenclamide 10 mg
    - c. Metformin 1000-1700 mg + glibenclamide 2.5 mg  $\rightarrow$  metformin 850 mg
    - d. Metformin 1000-1700 mg + glibenclamide 5 mg  $\rightarrow$  metformin 850 mg + glibenclamide 2.5 mg
    - e. Metformin 1000-1700 mg + glibenclamide 10 mg  $\rightarrow$  metformin 850 mg + glibenclamide 5 mg
    - f. Metformin 1000-1700 mg + glibenclamide 15-20 mg  $\rightarrow$  metformin 850 mg + glibenclamide 10 mg
    - g. Metformin 2000-2550 mg + glibenclamide 2.5 mg  $\rightarrow$  metformin 1700 mg
    - h. Metformin 2000-2550 mg + glibenclamide 5 mg  $\rightarrow$  metformin 1700 mg + glibenclamide 2.5 mg
    - i. Metformin 2000-2550 mg + glibenclamide 10 mg  $\rightarrow$  metformin 1700 mg + glibenclamide 5 mg
    - j. Metformin 2000-2550 mg + glibenclamide 15-20 mg → metformin 1700 mg + glibenclamide 10 mg

#### A1c >14 OR FBG >400

Coordinator/MD consult for all cases

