- Glycemic testing, vital signs, and other anthropometric data Fasting status, defined as no caloric intake for the past 8 hours, is determined. Blood glucose and hemoglobin A1c are collected for each patient. If hypoglycemia or severe hyperglycemia are identified at this stage, the application initiates management protocols (Appendix 4 and Appendix 5). CHWs also measure blood pressure, pulse (also collected by the automatic BP cuff), height, weight, and waist circumference. Hypotension or hypertension are addressed according to the protocol described in Appendix 12
- Screening for possible complications of diabetes (Appendix 6) The application guides CHWs through an
  assessment for possible complications of diabetes, including diabetic foot ulcers, angina, and diabetic eye
  disease.
- Recommendations for referrals (Appendix 7) Based on information collected and entered by the CHW, the application will make recommendations regarding the need for a referral to SLMH and evaluation the medical director [name]. Referral recommendations are classified as emergent (recommended immediate transport), urgent (evaluation by physician within 1-2 days), or routine (evaluation by physician within 1-2 weeks). CHWs are prompted by the application to immediately arrange for referral and transport for emergent conditions (e.g. current chest pain suspicious for angina) as soon as these conditions are identified. The recommendation for referral in these cases is a "hard stop" and the CHW will not be able to proceed with application questions until the emergent situation is addressed and

Version #: 1.0

[name]

definitive care arranged. These recommendations for referrals are consistent with the WHO protocol for diabetes management in low-resource settings  $^{\rm 47}$ 

Medication recommendations and counseling - Based on medication history, A1c, and glycemic goal, the
application uses an algorithm to determine a recommended medication regimen for the patient, including
the amount of medication to dispense (Appendix 8). The application provides information on how to take
the medication and how to avoid adverse effects, which the CHW discusses with the patient (Appendix 9).
The CHW then uses the "teach-back" method to ensure that the patient understands how to take their
medication. The CHW will also provide patient education on diabetes self-management, including diet,

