## **Appendix 5 - Hyperglycemia Protocols**

# Hyperglycemia

- 400≤FBG<HI
  - Urgent MD visit recommended in all cases
    - Patient willing to go
      - Dispense 5 days' worth of meds as a bridge based on 180(200)≤FBG<400 recommendations (if monthly visit) or A1c (month 3 or enrollment)
      - Arrange appointment
         Patient unwilling to go
        - Dispense medications based on 180(200)≤FBG<400 recommendations (if monthly visit) or A1c (month 3 or enrollment)
        - Follow up in 1-3 days
- FBG=HI

.

•

.

- Emergent visit recommended in all cases
  - Patient willing to  $go \rightarrow arrange emergency transport$
  - Patient not willing to go
    - Dispense medications based on 180(200)≤FBG<400 recommendations (if monthly visit) or A1c (month 3 or enrollment)
    - Follow up in 1 day
- PPBG=HI
  - "Is the patient unresponsive, very sleepy, or confused" (Y/N)
    - If YES, emergency visit recommended
      - Patient willing to  $go \rightarrow arrange emergency transport$
      - Patient not willing to go
        - Dispense medications based on 180(200)≤FBG<400 (if monthly visit) or A1c (month 3 or enrollment) recommendations
        - Follow up later that day or the next day
    - If NO
      - CHW advises patient to increase water intake
      - Dispense medications based on 180(200)≤FBG<400 recommendations (if monthly visit) or A1c (month 3 or enrollment)
      - Follow up with FBG in 1-3 days

Version #: 1.0

[name]

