# Indications for referrals

- Routine referrals
  - Stage I hypertension (BP 140-160/90-100 mmHg)
  - Non-infected diabetic ulcer
  - Need for renal function testing
  - A1c ≥9 despite maximal doses of metformin and glibenclamide for ≥3 months
  - A1c ≥9 for 3 consecutive checks
  - A1c above glycemic target, but less than 9 for 4 consecutive checks
  - Recent chest pain, moderate risk (2 of 5 points)
  - Blood in stool or possible melena
  - $\circ$   $\;$  Patient has other symptoms not addressed by the program protocols
  - Urgent referrals
    - Stage II hypertension (BP 160-200/100-120 mmHg)
    - Possibly infected diabetic ulcer, no signs of systemic infection
    - Worsening vision
    - FBG detectable, but ≥400
    - o A1c ≥14
    - Patient cannot tolerate minimum doses of metformin and/or glibenclamide
    - Current chest pain, moderate risk (2 of 5 points)
  - Emergency referrals
    - Severe hypertension (BP ≥200/120 mmHg)
    - Fasting blood glucose undetectable high
    - Postprandial/random blood glucose undetectable high with mental status changes
    - Hypoglycemia associated with altered mental status
    - Persistent hypoglycemia despite treatment in the field
    - Current chest pain, high risk (≥3 of 5 points)
    - o Possibly infected diabetic ulcer with signs of systemic infection

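### At enrollment, Appendix 5 has the community health worker dispense by A1c when fasting glucose is 400 or more, while Appendix 8 requires a consult and gives no regimen above 400

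*Combined protocol and SAP*

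**What the plan says.** Section 7.4.1 (Enrollment Visit) brings Appendix 5 into the first visit: "If hypoglycemia or severe hyperglycemia are identified at this stage, the application initiates management protocols". The same section lists medication history, A1c and glycemic goal as the inputs to the enrollment dosing algorithm. FBG is not among them.

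Appendix 5 (Hyperglycemia Protocols) gives these instructions:

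- **FBG from 400 up to but not including HI:** urgent physician visit for everyone. If the patient will go, "Dispense 5 days' worth of meds as a bridge based on" the A1c when the visit is enrollment or month 3. If not, "Dispense medications based on 180(200)≤FBG<400 recommendations (if monthly visit) or A1c (month 3 or enrollment" visit), with follow-up in 1-3 days.
- **FBG reads HI:** emergency visit. The CHW dispenses by A1c only if the patient refuses transport, with follow-up in 1 day.
- **Postprandial glucose (PPBG) reads HI:** the CHW dispenses by A1c if mental status is normal, or if it is altered and the patient refuses the emergency visit.

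Appendix 8 has dose rows up to and including A1c 14. Its last band, headed "A1c >14 OR FBG >400", contains one line: "Coordinator/MD consult for all cases". Appendix 11 (month 3) has the same single line for A1c above 14, without an FBG condition.

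Appendix 7 (Indications for referrals) makes "FBG detectable, but ≥400" an urgent referral, as it does an A1c of 14 or more. It makes "Fasting blood glucose undetectable high" an emergency referral.

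**The concern.** Appendices 5 and 8 both apply to the same patient at the same visit. One has the CHW hand over medication; the other sends the decision to a coordinator or physician and states no dose. The patients concerned are the most hyperglycemic enrollees, seen by CHWs who, as section 2.1 explains, act on what are in essence standing orders.

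The conflict also reaches the trial's measurements. Instances of an incorrect application recommendation are a primary safety endpoint (sections 4.1.3 and 10.1). Section 2.7.2 relies on alpha testing of every scenario to show that the application's output is correct. Both need one defined correct output per scenario, and for these patients the protocol gives two.

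**Working it through.** The plan states no figure on this point, so there is nothing to reproduce. The check applies the enrollment rules of the three appendices, as written, to readings on either side of each cut-off. HI is treated as above 400, because Appendix 5 places it above the band that starts at 400.

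| Enrollment readings | Appendix 5 | Appendix 7 | Appendix 8 | Result |
|---|---|---|---|---|
| FBG 399, A1c 12 | not triggered | none | 9-14 dose row | agree |
| FBG 400, A1c 12 | urgent visit, dispense by A1c | urgent | 9-14 dose row | trigger differs, same dose row |
| FBG 401, A1c 12 | urgent visit, dispense by A1c | urgent | consult, no dose | conflict |
| FBG HI, A1c 12, transport accepted | emergency transport | emergency | consult, no dose | no dispensing conflict |
| FBG HI, A1c 12, transport refused | dispense by A1c | emergency | consult, no dose | conflict |
| FBG 400 or 401, A1c 14.1 | urgent visit, dispense by A1c | urgent (both criteria) | consult, no dose | pointer reaches no dose |
| PPBG HI, A1c 14.1, normal mental status | dispense by A1c | urgent (A1c) | consult, no dose | pointer reaches no dose |
| FBG 399, A1c 14.0 | not triggered | urgent (A1c) | 9-14 dose row | both can be followed |
| FBG 399, A1c 14.1 | not triggered | urgent (A1c) | consult, no dose | agree |

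Four things follow.

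1. **Direct conflict.** It arises at enrollment for FBG above 400 and readable, and for FBG=HI when transport is refused. The result at FBG 401 is the same with A1c 8.5 or 14.0: an A1c dose row exists, Appendix 5 points to it, and the final band of Appendix 8 overrides it with a consult for all cases.
2. **Pointer without a dose.** When A1c exceeds 14, dispensing by A1c has no dose to draw on. This covers FBG of 400 or more, FBG=HI with refusal, and PPBG=HI with normal mental status or refusal. PPBG is not in the heading of the consult band, so a PPBG=HI patient reaches that line only through A1c above 14.
3. **Month 3.** Only the second problem carries over. Appendix 11 has no FBG condition on its consult line, so FBG of 400 or more with A1c up to 14 still leads to a dose row.
4. **Boundaries.** FBG of exactly 400 is inside Appendices 5 and 7 and outside the Appendix 8 consult band. A1c of exactly 14 is an urgent referral in Appendix 7 and an ordinary dosing case in Appendix 8. Neither mismatch by itself gives instructions that cannot both be followed.

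**The case against.** The strongest reply is that the two instructions add up: the CHW calls, the coordinator or physician decides, and the bridge supply follows. On that view the consult line deliberately hands the case to a person, and the telephone route in sections 2.1 and 7.4.1 supplies the dose. Physician review of each visit within a week (7.4.1) and the monthly check of recommendations (10.3) would catch any error.

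Part of this stands. The Appendix 8 line is an instruction, and a consult can produce a regimen. But Appendix 5 states its dispensing steps with no prior consult, and nothing gives the order. Where the protocol wants a dose and a consult together, or wants the physician to choose the drugs, it says so: the Appendix 10 band for FBG 180(200) to below 400 does each (items 17b and 25b). Section 2.1 offers telephone advice for questions and for situations outside the protocols, whereas these cases fall inside two of them. Review within a week comes after medication has been dispensed.

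Three stronger readings are tempting and are not supported.

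- A reader might infer that Appendix 8 has no entry for these patients. It has one; what it lacks is a dose.
- A reader might infer that Appendix 7 also takes patients out of CHW dosing, making a three-way conflict. Appendix 7 sets referral urgency only. Section 7.4.1 treats referral and medication as separate steps, and Appendix 5 itself combines urgent referral with dispensing.
- A reader might infer that everyone with FBG of 400 or more, or A1c of 14 or more, is affected. As the table shows, A1c above 14 without FBG of 400 or more or a HI reading is handled consistently, and so is FBG=HI when transport is accepted.

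**Conclusion.** The concern holds as an internal contradiction between Appendix 5 and Appendix 8 at enrollment, together with an Appendix 5 pointer that yields no dose when A1c exceeds 14 (Appendix 8 at enrollment, Appendix 11 at month 3). The differences at exactly 400 and exactly 14 are editorial.

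Its size cannot be estimated. The documents give neither the distribution of FBG nor a baseline mean A1c. A reader might try a normal tail from the SD of 2.4 in section 8.1. With an assumed mean of 9, (14 - 9)/2.4 = 2.08, or 1.9% at A1c 14 or more; with an assumed mean of 10, (14 - 10)/2.4 = 1.67, or 4.8%. That counts a different group: it includes patients whose instructions agree and omits those with FBG above 400 and a lower A1c. It should not be used as the magnitude.

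The finding rests on reading the appendices as the specification for the application, which is how section 2.3 describes them. It takes no view on which clinical instruction is right.

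**What to change.** Reconcile section 7.4.1 (Enrollment Visit), Appendix 5, Appendix 7, the 9-14 and final bands of Appendix 8, and the A1c above 14 line of Appendix 11. The revised text should:

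- state which passage governs when Appendix 5 and the dosing table both apply, and in what order the steps occur;
- state what the Appendix 5 reference to A1c means when A1c is above 14;
- use one boundary convention for FBG 400 and one for A1c 14 throughout;
- say whether FBG is an input to the enrollment dosing algorithm.

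The medical director decides the clinical content. The reconciled rule should then serve as the reference output for these cases in the alpha testing of section 2.7.2, and for scoring incorrect recommendations under section 4.1.3.

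The cost is appendix wording, the matching application logic and a rerun of the affected test cases. Sample size, visits and analyses do not change.

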#### **Appendix 9 - Medication Instructions**

# Metformin 850 mg

- For patients starting metformin
  - Start taking one 850 mg tablet with breakfast
    - After two weeks, start taking two tablets daily, one with breakfast and one with dinner
- Dosing
  - $\circ$  850 mg  $\rightarrow$  take one tablet per day with breakfast
  - $\circ$  1700 mg  $\rightarrow$  take two tablets daily, one with breakfast and one with dinner
  - $\circ$  2550 mg  $\rightarrow$  take three tablets daily, one with breakfast, one with lunch, and one with dinner
  - Guidance for patients experiencing metformin GI side effects
  - Always take metformin with food
    - Try taking metformin at night, instead of in the morning
    - Take half a tablet with breakfast and half a tablet with dinner (for patients taking one tablet per day)

Version #: 1.0

[name]

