## 2.6 Dose Rationale

The standard doses for metformin and glibenclamide used in our program are as follows:

- Metformin: 850 mg, 1500 mg, or 2550 mg per day (850 mg dosed once, twice, or three times daily, respectively)
- Glibenclamide: 2.5 mg, 5 mg, or 10 mg one time daily

In accordance with diabetes treatment guidelines, metformin is the first line medication for all patients in the program and is continued in all patients as long as it is tolerated and there are no contraindications. The standard starting dose of metformin in our protocol is 1700 mg (850 mg twice daily) as 1500 - 2000 mg is thought to be the usual effective dose range.

Also in accordance with ADA and AACE guidelines, patients with initial or repeat A1c ≥9% are placed on dual therapy with metformin and glibenclamide. For patients who are initially started on metformin alone and whose A1c is <9%, glibenclamide is added if they are not meeting glycemic targets despite maximum daily dose of metformin (2550 mg). Though the maximum dose of glibenclamide is 20 mg, most of the hypoglycemic effect of glibenclamide is thought to come at the initial 2.5 mg dose and doses above 10 mg per day are not thought to provide significant additional benefit. For this reason, the maximal dose of glibenclamide used in our program is 10 mg per day.

Glibenclamide does carry a higher risk of hypoglycemia compared to newer sulfonylureas such as glimepiride and glipizide. However, glibenclamide was selected for use in this program because other sulfonylureas are either not readily available in Guatemala or are prohibitively expensive compared to glibenclamide. In addition, though glibenclamide carries a higher hypoglycemia risk than other sulfonylureas, the risk of serious 15

[name]

hypoglycemia (requiring the assistance of another person or hospitalization) is still low, with reported occurrence in only 0.5% of patients in a meta-analysis of sulfonylurea studies.

The application will recommend aspirin for patients with a history of ischemic stroke and CAD to prevent recurrent events and for patients with possible ACS, as long as contraindications are not present. The dose used for ASCVD prevention is 81 mg per day, which is in accordance with current consensus guidelines. The dosage used for treatment of possible ACS is 324 mg, also in accordance with current consensus guidelines.

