# 6.5 Starting Dose and Dose Escalation Schedule

Metformin will be started at 850 mg once daily and increased to the target dose of 1700 mg after 2 weeks. If not meeting treatment goals after ≥1 month, metformin can be increased to 2550 mg. Patients who are unable to tolerate the 1700 mg dose will take the 850 mg dose.

Version #: 1.0

[name]

Glibenclamide will be used for patients who are unable to tolerate metformin, in addition to metformin if A1c  $\geq$ 9, or if glycemic goals not met despite maximal dose of metformin. Dosing will start at 2.5 mg once per day. If glycemic goals are not met after  $\geq$ 1 month, dose will be escalated to 5 mg once per day and then 10 mg once per day as needed.

Aspirin will be dosed at 81 mg once per day for secondary prevention in eligible patients with history of MI or stroke or patients who have new chest pain and are awaiting medical workup for possible CAD. Patients with high risk chest pain and possible ACS will be treated with aspirin 324 mg (four 81 mg tablets) once while awaiting emergency transport to SLMH.

Please consult Appendix 8, Appendix 10, and Appendix 11 for further information on medication titration protocols

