#### Tx goal< A1c <9

- Not taking medications or nonadherent, no hypoglycemia or hypoglycemia symptoms, no problems with metformin → metformin 1700 mg
- 2. Not taking medications or nonadherent, no hypoglycemia or hypoglycemia symptoms, problems with metformin
  - a. Agrees to take metformin  $\rightarrow$  metformin 850 mg + glibenclamide 2.5 mg
  - b. Refuses to take metformin  $\rightarrow$  glibenclamide 2.5 mg
- 3. Not taking medications or nonadherent, hypoglycemia or hypoglycemia symptoms → metformin 1700 mg
- 4. Not taking medications or nonadherent, hypoglycemia or hypoglycemia symptoms, problems with metformin
  - a. Agrees to take metformin  $\rightarrow$  metformin 850 mg
  - b. Refuses to take metformin, prescribed glibenclamide >2.5 mg  $\rightarrow$  glibenclamide 2.5 mg
  - c. Refuses to take metformin, prescribed glibenclamide 2.5 mg  $\rightarrow$  MD consult
- 5. Taking metformin without problems
  - a. Metformin 500-1000 mg  $\rightarrow$  metformin 1700 mg
  - b. Metformin 1500-2000 mg → metformin 2550 mg
  - c. Metformin 2550 mg  $\rightarrow$  metformin 2550 mg + glibenclamide 2.5 mg
- 6. Taking metformin with problems
  - a. Metformin 500-850 mg, agrees to take metformin → metformin 850 mg + glibenclamide 2.5 mg

[name]

- b. Metformin 500-850 mg, refuses to take metformin  $\rightarrow$  glibenclamide 2.5 mg
- c. Metformin 1000-1700 mg  $\rightarrow$  metformin 850 mg + glibenclamide 2.5 mg
- d. Metformin 2000-2550 mg  $\rightarrow$  metformin 1700 mg + glibenclamide 2.5 mg
- 7. Taking glibenclamide without problems
  - a. Glibenclamide 2.5-10 mg  $\rightarrow$  metformin 1700 mg + glibenclamide current dose
  - b. Glibenclamide 15-20 mg → metformin 1700 mg + glibenclamide 10 mg
- 8. Taking glibenclamide, previous problems with metformin
- a. Agrees to take metformin
  - i. Glibenclamide 2.5-10 mg  $\rightarrow$  metformin 850 mg + glibenclamide current dose
  - ii. Glibenclamide 15-20 mg  $\rightarrow$  metformin 850 mg + glibenclamide 10 mg
  - b. Refuses to take metformin
    - i. Glibenclamide 2.5 mg  $\rightarrow$  glibenclamide 5 mg
    - ii. Glibenclamide 5 mg  $\rightarrow$  glibenclamide 10 mg
- iii. Glibenclamide 10-20 mg  $\rightarrow$  glibenclamide 10 mg
- 9. Taking glibenclamide with hypoglycemia or hypoglycemia symptoms
  - a. Glibenclamide 2.5 mg  $\rightarrow$  metformin 1700 mg
  - b. Glibenclamide 5 mg  $\rightarrow$  metformin 1700 mg + glibenclamide 2.5 mg

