#### 9≤ A1c ≤14

- 1. Not taking medications  $\rightarrow$  metformin 1700 mg + glibenclamide 2.5 mg
- 2. Not taking medications, problems with metformin
  - a. Agrees to take metformin → metformin 850 mg + glibenclamide 2.5 mg
  - b. Refuses to take metformin  $\rightarrow$  glibenclamide 2.5 mg
- 3. Not taking medications, hypoglycemia or hypoglycemia symptoms  $\rightarrow$  metformin 1700 mg
- 4. Not taking medications, hypoglycemia or hypoglycemia symptoms, problems with metformin
  - a. Agrees to take metformin, prescribed glibenclamide >2.5 mg  $\rightarrow$  metformin 850 mg + glibenclamide 2.5 mg
  - b. Agrees to take metformin, prescribed glibenclamide 2.5 mg  $\rightarrow$  metformin 850 mg
  - c. Refuses to take metformin, prescribed glibenclamide >2.5 mg  $\rightarrow$  glibenclamide 2.5 mg
  - d. Refuses to take metformin, prescribed glibenclamide 2.5 mg  $\rightarrow$  MD consult
- 5. Taking metformin without problems
  - a. Metformin 500-2000 mg  $\rightarrow$  metformin 1700 mg + glibenclamide 2.5 mg
  - b. Metformin 2550 mg  $\rightarrow$  metformin 2550 mg + glibenclamide 2.5 mg
- 6. Taking metformin with problems
  - a. Metformin 500-850 mg, agrees to take metformin  $\rightarrow$  metformin 850 mg + glibenclamide 2.5 mg
  - b. Metformin 500-850 mg, refuses to take metformin  $\rightarrow$  glibenclamide 2.5 mg
  - c. Metformin 1000-1700 mg  $\rightarrow$  metformin 850 mg + glibenclamide 2.5 mg
  - d. Metformin 2000-2550 mg  $\rightarrow$  metformin 1700 mg + glibenclamide 2.5 mg
- 7. Taking glibenclamide without problems
  - a. Glibenclamide 2.5-10 mg → metformin 1700 mg +glibenclamide current dose
  - b. Glibenclamide 15-20 mg  $\rightarrow$  metformin 1700 mg + glibenclamide 10 mg
- 8. Taking glibenclamide without problems, previous problems with metformin
  - a. Agrees to take metformin
    - i. Glibenclamide 2.5-10 mg → metformin 850 mg + glibenclamide current dose
    - ii. Glibenclamide 15-20 mg  $\rightarrow$  metformin 850 mg + glibenclamide 10 mg
  - b. Refuses to take metformin
    - i. Glibenclamide 2.5 mg  $\rightarrow$  glibenclamide 5 mg
    - ii. Glibenclamide 5 mg  $\rightarrow$  glibenclamide 10 mg
    - iii. Glibenclamide 10-20 mg  $\rightarrow$  glibenclamide 10 mg
- 9. Taking glibenclamide with hypoglycemia or hypoglycemia symptoms
  - a. Glibenclamide 2.5 mg  $\rightarrow$  metformin 1700 mg
    - b. Glibenclamide 5 mg  $\rightarrow$  metformin 1700 mg + glibenclamide 2.5 mg

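### The metformin start differs between section 2.6 and section 6.5/Appendix 9, and Appendix 9 gives patients whom Appendix 8 assigns to 850 mg two incompatible instructions

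*Combined protocol and SAP*

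**What the plan says.** Four places in the combined protocol and SAP describe how metformin begins.

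- **Section 2.6 (Dose Rationale)** says "The standard starting dose of metformin in our protocol is 1700 mg (850 mg twice daily" and mentions no step-up. Just before that, it lists the dose levels as "Metformin: 850 mg, 1500 mg, or 2550 mg per day (850 mg dosed once, twice, or three times daily, respectively".
- **Section 6.5 (Starting Dose and Dose Escalation Schedule)** says "Metformin will be started at 850 mg once daily and increased to the target dose of 1700 mg after 2 weeks". It adds "Patients who are unable to tolerate the 1700 mg dose will take the 850 mg dose".
- **Appendix 8 (enrollment dosing)** gives single daily doses with no step-up. For treatment goal < A1c < 9, the first row reads "Not taking medications or nonadherent, no hypoglycemia or hypoglycemia symptoms, no problems with metformin → metformin 1700 mg". Patients with metformin problems who accept the drug get 850 mg. In the 9 to 14 band, for example, the branch "Not taking medications, problems with metformin" leads to "Agrees to take metformin → metformin 850 mg + glibenclamide 2.5 mg".
- **Appendix 9 (Medication Instructions)** has a block for patients starting metformin: one 850 mg tablet with breakfast, then "After two weeks, start taking two tablets daily, one with breakfast and one with dinner". No exception is written. A separate Dosing list directly below it gives one tablet a day for 850 mg, two for 1700 mg and three for 2550 mg.

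Under the enrollment visit in section 7, the application sets the regimen and quantity from Appendix 8 and supplies the Appendix 9 information. The CHW discusses that information with the patient and checks it by teach-back.

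**The concern.** Two things do not fit together. First, for an ordinary new starter, section 2.6 implies 1700 mg from the first day, whereas section 6.5 and Appendix 9 imply 850 mg for two weeks. Second, Appendix 8 holds patients with metformin problems at 850 mg, while the Appendix 9 start block, read literally, moves anyone who is starting to two tablets in week 3.

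This is operative text, relayed by CHWs without a physician present. The second conflict falls on patients who have already had trouble with the drug. It also touches measurement. Metformin adverse effects and medication adherence are secondary endpoints (section 4.1.2), and incorrect application recommendations are a primary safety endpoint (section 4.1.3). While the specification conflicts with itself, testing the application cannot establish which message is correct for these patients.

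**Working it through.** The claim rests on no power, alpha or event figure. The check is a comparison of texts plus dose and tablet arithmetic.

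**1. Dose levels.** Daily dose = tablets per day x 850 mg.

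- 1 x 850 = 850 mg, which matches section 2.6.
- 2 x 850 = 1700 mg. Section 2.6 lists 1500 mg here, but gives 1700 mg for the same twice-daily regimen in its next paragraph.
- 3 x 850 = 2550 mg, which matches section 2.6.

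Only the middle entry fails.

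**2. Versions of the start for a patient without metformin problems.**

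| Source | Days 1 to 14 | From day 15 |
|---|---|---|
| Section 2.6 | 1700 mg | 1700 mg |
| Appendix 8, read literally | 1700 mg | 1700 mg |
| Section 6.5 | 850 mg | 1700 mg |
| Appendix 9 start block | 850 mg | 1700 mg |

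There are two versions. They differ two-fold for 14 days (28 tablets against 14) and agree afterwards.

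**3. Patients assigned 850 mg because of metformin problems.** These Appendix 8 rows cover patients who accept metformin and are listed either as not taking medication (in some rows, or nonadherent) or as on glibenclamide only. The number of outcome lines giving 850 mg, alone or with glibenclamide, is:

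- A1c < 5.7: items 6a and 7a, 2 lines
- 5.7 to < 6.5: item 6a, 1 line
- 6.5 to goal: items 2a, 3a, 7a and 9a, 1 + 1 + 4 + 4 = 10 lines
- goal to < 9: items 2a, 4a, 8a and 10a, 1 + 1 + 2 + 4 = 8 lines
- 9 to 14: items 2a, 4a, 4b, 8a and 10a, 1 + 1 + 1 + 2 + 4 = 9 lines

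The total is 2 + 1 + 10 + 8 + 9 = 30 lines by hand count. None states a step-up. These are branches of the algorithm, not patients; the documents do not say how many patients would fall in them.

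**4. What Appendix 9 tells such a patient.** Under the Dosing list, 850 mg means one tablet a day throughout. Under the start block, it is one tablet a day for two weeks and then two. No text ranks the two, and none says whether resuming metformin after earlier problems counts as starting it.

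**5. Size of the discrepancy if the start block is followed.** Over d days, with one tablet for 14 days and two thereafter, tablets = 14 + 2(d - 14). The monthly interval is taken as 28 to 31 days, an assumption.

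| Days | Fixed 850 mg | Start block | 1700 mg from day 1 |
|---|---|---|---|
| 28 | 28 | 14 + 28 = 42 | 56 |
| 30 | 30 | 14 + 32 = 46 | 60 |
| 31 | 31 | 14 + 34 = 48 | 62 |

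From day 15 the dose taken is 1700 / 850 = 2 times the dose assigned.

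**The case against.** The best defence is that these texts can mostly be read together. Section 2.6 is a rationale; it justifies 1700 mg by the usual effective range and may simply be naming the target, which is what section 6.5 calls that dose. The flat 1700 mg in Appendix 8 can be read the same way, with Appendix 9 explaining how to reach it. The 1500 mg entry looks like a slip, since every twice-daily dose assigned in Appendices 8, 10 and 11 is 1700 mg. Section 6.5 provides for 850 mg in intolerance, and the Appendix 9 Dosing list has a matching one-tablet line. The application uses skip logic (section 2.3) and may show only the instruction that fits. Someone who has taken metformin before may not be a starter at all, and some of the Appendix 8 rows include patients nonadherent to an existing prescription.

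Much of this stands, and it rules out several stronger readings that a reader might infer:

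- *The start is written three ways.* For an ordinary starter there are two versions, because section 6.5 and Appendix 9 agree. The flat 850 mg belongs to a different group.
- *Appendix 9 sends every starter to two tablets and overrides Appendix 8.* The Dosing list points the other way, so Appendix 9 is in conflict with itself for these patients; nothing says that the start block prevails.
- *CHWs will read out a dose that differs from the one dispensed.* The display rules are not given, so this is possible but not established.
- *Patients will run out early, and the algorithm will then titrate on side effects or non-adherence that the instructions caused.* With an assumed 30 tablets, the supply would last 14 + 16/2 = 22 days. But the documents give no tablet count for these rows, and the later steps have no estimate behind them.

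The defence does not remove the conflict. Section 2.6 uses the word starting for 1700 mg. The start block carries no exception, and the intolerance clause in section 6.5 is not repeated there. Patients on glibenclamide only are not taking metformin, so starting or resuming it is the ordinary description of what Appendix 8 asks of them. Physician review within a week of the visit would fall before day 15, but it is described as a review of the visit summary, and nothing says that this shows the instruction given.

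**Conclusion.** The inconsistency is real and should be resolved before CHWs rely on the text. Section 2.6 disagrees with section 6.5 and Appendix 9 on the first two weeks, by a factor of two, and its 1500 mg entry contradicts its own description. Patients assigned 850 mg who are starting or resuming metformin have two incompatible Appendix 9 instructions and no rule for choosing.

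If such a patient follows the start block, the dose is twice the assigned one from day 15, or 16 extra tablets in 30 days (14 to 17 over 28 to 31 days). That figure assumes a visit interval of 28 to 31 days, full adherence to the start block and enough tablets to follow it. The number of patients affected is unknown, and no effect on the A1c endpoints is shown. The finding is a contradiction in safety-relevant dosing text, not evidence that any patient would be misdosed.

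**What to change.** Reconcile section 2.6, section 6.5, Appendix 8 and Appendix 9, so that each describes the same start for the same patient. Specifically:

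1. State in section 2.6 whether 1700 mg is the dose on day 1 or the target, in agreement with section 6.5.
2. Correct or explain the 1500 mg entry.
3. State which Appendix 9 instruction applies to a patient whom Appendix 8 assigns to 850 mg.
4. Define whether resuming metformin after earlier problems counts as starting it.
5. Describe which Appendix 9 text the application displays for each Appendix 8 outcome, and check the programmed messages against it.

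Which schedule should prevail is a clinical decision for the investigators and the medical director, and none is proposed here. The cost is protocol wording and possibly one changed message in the application; the design, sample size and analysis are unaffected.
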